7.1 Effectiveness Measures

7.1.1 Primary Effectiveness Measure

The primary effectiveness measure is the volume change from baseline in the nose area as calculated by digital analysis of each subject's 3D images.

7.1.2 Secondary Effectiveness Measures

Secondary effectiveness measures include the EI's and subject's assessments of aesthetic improvement of the nose using the 5-point GAIS (Table 4), and subject's assessment of treatment outcome using the 5-point NSS (Table 5).

Table 4 5-Point Global Aesthetic Improvement Scale

Score	Grade	Description
2	Much improved	Marked improvement in appearance
1	Improved	Improvement in appearance, but a touch-up or retreatment is indicated
0	No change	The appearance is essentially the same as the original condition
-1	Worse	The appearance is worse than the original condition
-2	Much worse	The appearance is much worse than the original condition

Table 5 5-Point Nose Satisfaction Scale

Score	Grade
+2	Very satisfied
+1	Satisfied
0	Neutral (neither satisfied or dissatisfied)
-1	Dissatisfied
-2	Very dissatisfied

The 56-day post-treatment subject diary will list the following severities for ISRs to be recorded:

Mild	Symptoms causing little, if any, discomfort leading to little, if any, effect on daily activities.
Moderate	Symptoms causing some discomfort leading to some effect on daily activities.
Severe	Symptoms causing great discomfort leading to compromised performance of daily activities.

The TI (or designee) will review the 56-day post-treatment subject diary and discuss any unusual signs/symptoms with the subject. If an ISR of initial treatment is ongoing at the touch-up treatment, it will be recorded and followed in the touch-up 56-day post-treatment subject diary. If an ISR is ongoing at the end of the safety diary after the last treatment, the TI (or designee) will continue to follow the ongoing ISR to resolution via the recommended weekly evaluation and will document the entire course of the ISR on the Ongoing ISR form (ISR type, severity [mild, moderate, or severe], ISR start date, and ISR end date) in the eCRF.

7.3 Demographics and Baseline Characteristics

Subject demographics and baseline characteristics to be collected include sex, age, race, medical/surgical/cosmetic/dental procedure history, and prior medications.

7.4 Treatment Characteristics

Treatment characteristics will be evaluated by collecting information on anesthesia usage (ice, lidocaine cream, local anesthesia, nerve block), injection site (midline dorsum, columella, and anterior spine), injection plane (supraperiosteally and supraperichondrially), injection volume, injection ease (11-point scale where 0 = difficult and 10 = easy), and product moldability (11-point scale where 0 = stiff and 10 = moldable).

7.5 Summary of Methods of Data Collection

Electronic data capture will be used to collect study-specific information, such as subject and investigator assessments. Completed eCRFs will be reviewed by the TI or EI as applicable (or designee), and the designated monitor will verify the data. Investigators will provide access to hospital files, medical records, and other source documents containing subject clinical/medical information. Source document verification will be performed.

Treatment and safety assessments will be performed by the TI. The initial treatment and touch-up treatment (if performed) for each subject must be performed by the same TI. The effectiveness assessments for each subject are strongly recommended to be performed by the same EI throughout the study. The blinded independent technician will be responsible for all 3D digital image analyses which will be used as effectiveness assessments. At specified timepoints, subjects will complete questionnaires and 56-day post-treatment subject diary(ies).

After signing the ICF and until exit from the study, any untoward signs or symptoms or other AEs as well as concomitant medications, procedures and therapies of all subjects (treatment and control groups) will be carefully monitored by the TI and documented by either the TI or assigned site staff.

Subjects will complete the paper ISR diaries, and responses will be entered into the clinical database.

Canfield Scientific will be responsible for analyzing 3D digital imaging data by independent, blinded technicians. Sites will save photographs onto supplied electronic media and send the storage device to Canfield Scientific. Alternatively, files containing the facial digital photographs may be directly uploaded to Canfield Scientific from the Canfield Scientific equipment.

8. Statistical Procedures

Allergan developed the statistical design of this trial. A separate statistical analysis plan will be prepared to provide specifications for all analyses. The plan will be finalized and approved prior to clinical database lock.

Descriptive statistics will be presented for key outcome measures. Categorical variables will be summarized with frequency and relative frequency. Continuous variables will be summarized by number of subjects, mean, median, standard deviation, minimum, and maximum. Where appropriate, 2-sided 95% CIs for population mean, or population proportion, will be provided as part of the descriptive summary.

Every attempt will be made to collect complete data and limit the occurrence of missing data. Imputation of missing data will be performed for the primary effectiveness analysis as a sensitivity analysis.

8.1 Analysis Populations

The following analysis populations will be used in the analyses for this study:

- modified intent-to-treat (mITT) population: subjects who are randomized to study treatment, receive at least 1 study device treatment and complete at least 1 effectiveness assessment (Treatment Group); and subjects who are randomized to no treatment and complete at least 1 effectiveness assessment (Control Group)
- per-protocol (PP) population: all mITT subjects who do not have any significant protocol deviations affecting the primary effectiveness endpoint
- safety population: subjects who receive at least 1 study treatment

Unless specified otherwise, effectiveness analyses and baseline characteristics will be conducted using the mITT population. The PP population will be used to perform sensitivity analyses for the primary effectiveness variable. All safety analyses will be conducted using the safety population. Control subjects' data after treatment will also be summarized.

8.2 Collection/Derivation of Primary and Secondary Effectiveness Assessments

8.2.1 Primary Effectiveness Variable

The primary effectiveness variable is the mean change in volume in subject's nose area from baseline as calculated by digital analysis of each subject's 3D images, where baseline is the pretreatment image at the randomization visit for the treatment group and the control group.

The primary effectiveness endpoint is the comparison of the mean change in nose area volume from baseline to the Week 24 visit for the treatment group versus that for the control group prior to treatment.

8.2.2 Secondary Effectiveness Variables

Secondary effectiveness variables include:

- The responder rate for the treatment group based on the GAIS assessment by the EI, which is defined as the percentage of subjects who note improvement (Improved or Much Improved) on the GAIS
- The responder rate for the treatment group based on the GAIS assessment by the subject, which is defined as the percentage of subjects who note improvement (Improved or Much Improved) on the GAIS

- The responder rate for the treatment group based on the NSS assessment by the subject, which is defined as the percentage of subjects who note satisfaction (Satisfied or Very Satisfied) on the NSS

8.3 Hypothesis and Methods of Analysis

8.3.1 Primary Effectiveness Analyses

The primary effectiveness endpoint is the comparison of mean change in volume in nose area based on 3D imaging between the treatment group and the control group (prior to treatment) at Week 24. The following hypothesis will be tested:

$$H_0: \mu_T = \mu_C \text{ versus } H_a: \mu_T \neq \mu_C$$

where μ_T and μ_C denote the mean change in volume since baseline for the treatment group and control group, respectively, at Week 24.

A 2-sided 2-group t-test (or Wilcoxon rank-sum test as appropriate) will be performed at the 5% level to test whether the mean volume change from baseline in the nose area for the treatment group is significantly greater than that for the control group at Week 24.

8.3.2 Secondary Effectiveness Analyses

Secondary effectiveness analyses will include:

- The observed responder rate with 95% exact CI at Week 24 for the treatment group based on the GAIS assessment by the EI
- The observed responder rate with 95% exact CI at Week 24 for the treatment group based on the GAIS assessment by the subject
- The observed responder rate with 95% exact CI at Week 24 for the treatment group based on the NSS assessment by the subject

A “responder” is defined as a subject who shows improvement in the overall aesthetic assessment (Improved or Much improved on GAIS) posttreatment. Since the GAIS assessments are only collected after treatment, there will be no data for the no-treatment control period for the control subjects. Responder analyses will be done for each treatment group separately. Responder analysis of the NSS will be similar to the GAIS. A “responder” is defined as a subject with a score of ≥ 1 point (Satisfied or Very satisfied) at Week 24 on the NSS.

[REDACTED]

8.3.4 Safety Analyses

ISRs will be summarized by treatment (initial and touch-up), incidence, severity, and duration. Incidence of AEs will be tabulated by primary system organ class (SOC) and by preferred term, and will be tabulated by onset, duration, severity, action taken, relationship to treatment, and outcome. Treatment-related AEs, SAEs, AEs leading to study discontinuations, and deaths will be listed or tabulated. Procedural pain, vital signs and laboratory results will be summarized by frequency distributions or descriptive statistics.

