Effectiveness: The primary effectiveness analysis is the mean volume change from baseline in nose area as calculated by digital analysis of 3D images at Week 24 (primary timepoint). A 2-sided, 2-sample t-test (or Wilcoxon rank-sum test, as appropriate) at a 5% significance level will be used to test whether the mean volume change from baseline in nose area for the treatment group is significantly greater than that for the control group at Week 24.

Secondary effectiveness analyses are responder analyses of EIs' and subjects' assessment of aesthetic improvement of the nose using the 5-point GAIS and subjects' assessment of NSS at Week 24. A "responder" is defined as a subject who shows improvement in the overall aesthetic assessment (Improved or Much improved on GAIS) posttreatment. Since the GAIS assessments are only collected after treatment, there will be no data for the control group subjects during the no-treatment control period. Responder analyses will be done for each treatment group separately. Responder analysis of NSS will be similar to GAIS. A "responder" is defined as the subject with a score of ≥ 1 point (satisfied or very satisfied) at Week 24 on the NSS.

Safety: Procedural pain will be summarized using descriptive statistics. ISRs reported in subject diaries will be summarized by treatment (initial and touch-up), symptom, severity, and duration. Summaries will include the incidence rate for each ISR.

AEs will be summarized by system organ class and preferred term and will be tabulated by onset, duration, severity, action taken, relationship to treatment, and outcome. Treatment-related AEs, serious AEs, AEs leading to study discontinuations, and deaths will be listed or tabulated.

[figure not shown]
Table of Contents

Synopsis	3
Table of Contents	8
List of Tables.....	11
1. Abbreviations and Terms.....	17
2. Background, Risk and Benefit, and Clinical Rationale.....	18
2.1 Background	18
2.2 Risk and Benefit.....	19
2.3 Clinical Rationale.....	19
3. Study Objectives and Clinical Hypotheses.....	20
3.1 Study Objectives	20
3.2 Clinical Hypotheses	20
4. Study Design.....	20
4.1 Structure	20
4.2 Duration	21
4.3 Treatment Groups and Treatment Regimen	21
4.3.1 Study Treatment	21
4.3.2 Control Treatment	21
4.3.3 Methods for Blinding	21
4.3.4 Touch-up Treatment Criteria.....	21
4.4 Permissible and Prohibited Medications/Treatments.....	22
4.4.1 Permissible Medications/Treatments	22
4.4.2 Prohibited Medications/Treatments	22

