4.3.3 Methods for Blinding

Neither the TI nor the subject will be blinded to treatment.

The Evaluating investigator (EI) will remain blinded to treatment assignment throughout the study. The blinded independent Canfield Scientific technician will be responsible for all 3D digital image analyses which will be used for the effectiveness evaluation.

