11.1.8 Relationship to Treatment

Relationship to treatment refers to a determination of the relationship (if any) between an AE and the device or treatment procedure. An AE could be considered treatment-related when, in the judgment of the TI, it is reasonable to believe that the event may have been caused by the device or is associated with the procedure, such as an event that can be attributed to other products, surgical techniques, or medications required specifically for the procedure.

Relationship to treatment must be determined by the TI and cannot be delegated to other study staff.

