5.6.3. Adverse Events

An AE will be considered a TEAE if the AE began or worsened (increased in severity or became serious) on or after the date (and time, if known) of the initial treatment for treatment group and after randomization for control group.

An AE will be considered a TESAE if it is a TEAE that additionally meets any SAE criterion.

TEAEs will be summarized by treatment group for CP using the Safety population.

TEAEs will also be summarized for TP using VITP and VOTP, respectively.

The number and percentage of participants with TEAEs as well as the events in the following AE categories will be summarized for the above populations as described in Table 5-7.

If more than 1 AE is coded to the same preferred term for the same participant, the participant will be counted only once for that preferred term using the most severe and most related occurrence for the summarizations by severity and by relationship to study intervention.

Listings of all TEAEs, TESAEs, TEAEs leading to discontinuation, and death will be presented.

Table 5-7 TEAE Summaries

| Endpoint | Description | Timing | Methodology |
|--------------------------------|--|--------|--|
| Overall summary | Overall summary only for the following categories: TEAEs Treatment-related TEAEs Treatment-related TEAEs at injection site Treatment-related TEAEs not at injection site TESAEs Treatment-related TESAEs Treatment-related TESAEs Treatment-related TESAEs at injection site Treatment-related TESAEs not at injection site Discontinued due to TEAE Deaths | CP, TP | Categorical descriptives, event descriptives |
| TEAEs | Overall summary and by SOC and PT Overall summary and by SOC, PT, and maximum severity | CP, TP | Categorical descriptives, event descriptives |
| Treatment-related TEAEs | Overall summary and by SOC and PT Overall summary and by SOC, PT, and maximum severity Overall summary by maximum severity, time to onset, duration, action taken and outcome | CP, TP | Categorical descriptives, event descriptives |
| TESAEs | Overall summary and by SOC and PT | CP, TP | Categorical descriptives, event descriptives |
| AEs leading to discontinuation | Overall summary and by SOC and PT | CP, TP | Categorical descriptives, event descriptives |

SAP 1894-701-008 amendment 1

5.6.4. **Injection Site Response**

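### The SAP limits the adverse event summaries of onset, duration, action taken and outcome to treatment-related events, although the protocol plans them for adverse events in general, and it does not declare the change

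*Protocol*

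**What the plan says.** Protocol 8.3.4 promises AE incidence by system organ class and preferred term (SOC/PT) and adds that AEs "will be tabulated by onset, duration, severity, action taken, relationship to treatment, and outcome". The safety paragraph of the synopsis makes the same promise, again with outcome as the last item: "AEs will be summarized by system organ class and preferred term and will be tabulated by onset, duration, severity, action taken, relationship to treatment, and". The next sentence of 8.3.4 deals with narrower sets as a separate item: "Treatment-related AEs, SAEs, AEs leading to study discontinuations, and deaths will be listed or tabulated".

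SAP 5.6.3, Table 5-7, turns this into rows. The row for all TEAEs reads "Overall summary and by SOC and PT Overall summary and by SOC, PT, and maximum severity". The row for treatment-related TEAEs has those two summaries and a third: "Overall summary by maximum severity, time to onset, duration, action taken and outcome". The rows for serious TEAEs and for AEs leading to discontinuation have SOC/PT only. All rows are scheduled for both the Control Period (CP) and the Treated Period (TP).

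On attribution, Protocol 11.1.8 states: "Relationship to treatment must be determined by the TI and cannot be delegated to other study staff". Protocol 4.3.3 states: "Neither the TI nor the subject will be blinded to treatment". TI is the treating investigator. SAP Appendix 2 (section 6.2), which lists departures from the protocol's analyses, covers the mixed model for the primary endpoint and the mITT and PP definitions. It does not mention AE tables.

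**The concern.** Onset, duration, action taken and outcome are the descriptors that show whether an event came late, persisted, needed intervention or failed to resolve. The protocol gives a reader reason to expect them for AEs as a whole. Under the SAP, an event enters these summaries only if the TI has called it related. The TI knows the assignment and, under Protocol 12.5.3, is the only person who may give the injection.

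The restriction also removes the untreated arm from these four descriptors. The trial follows a concurrent control for safety, and the SAP counts control events after randomization as TEAEs. Relatedness is defined against the device or the treatment procedure, however, and a control receives neither during the CP. What is at stake is a promised descriptive output and the background against which it could be read. No hypothesis test, error rate or data collection is affected.

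**Working it through.** The plan states no figure on this point, so the check sets the texts side by side.

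**1. Scope of the protocol sentence.** It cannot mean related events only. Relationship is one of the descriptors by which AEs are to be split, which would be pointless if unrelated events were already excluded. Treatment-related AEs are then named separately in the following sentence.

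**2. Descriptor by descriptor.** SAP time to onset is taken as the protocol's onset.

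| Descriptor | Protocol 8.3.4, AEs | Table 5-7, all TEAEs | Table 5-7, treatment-related TEAEs |
|---|---|---|---|
| Onset | yes | no | yes |
| Duration | yes | no | yes |
| Severity | yes | yes (maximum, within SOC/PT) | yes |
| Action taken | yes | no | yes |
| Relationship | yes | through the separate related rows | defines the row |
| Outcome | yes | no | yes |

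Six descriptors are promised. Severity and relationship survive in some form for all TEAEs, so 6 − 2 = 4 do not. Those four appear in the treatment-related row and in no other.

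**3. Who sets the filter.** The TI alone (Protocol 11.1.8), unblinded (4.3.3).

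**4. The control column.** SAP Table 4-1 places untreated controls with at least one follow-up assessment in the Safety Population, and SAP 5.6.3 starts their TEAEs after randomization. Control events therefore exist in the analysis set, and "TEAEs will be summarized by treatment group for CP using the Safety population". Protocol 4.3.2 gives controls no treatment in the CP, so no event of theirs can meet the definition in Protocol 11.1.8. The treatment-related row is scheduled for the CP, but its control column should be empty by construction.

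**5. Whether the data support a wider table.** SAP 6.4.2.1 imputes incomplete start dates against initial injection for the treatment group and randomization for controls. SAP 6.4.2.2 imputes end dates. Neither is limited to related events. Protocol section 11 puts severity, action taken and relationship on the AE form. Outcome is already needed for the related row.

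**6. Observation time.** In SAP Table 5-1 the treatment arm's CP runs from initial treatment to the Week 24 assessment, which is counted from the last treatment. Without a touch-up that is about 24 weeks. With one at 8 weeks it is 8 + 24 = 32 weeks. The control CP is about 24 weeks from randomization. The difference is 32 − 24 = 8 weeks, so any by-arm table needs a note.

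**The case against.** The strongest reply is that little is lost.

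- Every TEAE, whatever its attribution, enters the SOC/PT and maximum-severity tables by arm. Where applicable it also enters the serious-event, discontinuation and death summaries. An excess over control of events called unrelated would be visible there.
- All TEAEs are listed.
- Expected local reactions are recorded daily by the subject for 56 days after each treatment. SAP 5.6.4 tabulates their severity and duration and lists ongoing ones, with no stated relatedness filter.
- The threshold in Protocol 11.1.8 is low: a reasonable belief that the event may have been caused by the device, or that it is associated with the procedure.
- SAP section 1 says that table and listing specifications are held in a separate document. It was not available and may already contain the missing summaries.
- A by-arm comparison would rest on unequal observation time.

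All of this stands as a limit on the point. It does not remove it. A listing is not the tabulation that the protocol describes, and the SAP does not state its columns. The diary covers only predefined symptoms within its 56 days. If the shells do contain the tables, Table 5-7 is still out of step with them. Unequal follow-up calls for a footnote.

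A reader might infer that an effect wrongly judged unrelated would surface only in a listing, or that controls offer no safety comparison at all. The incidence and severity tables contradict both. A reader might also infer that the protocol promised a control column for these descriptors. It did not: Protocol 8.1 limits its safety population to treated subjects, and it is the SAP's wider Safety Population that makes a control column possible. Nor do the documents show that the TI's attributions are biased. They show only that the attributions are unblinded and undelegated.

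**Conclusion.** The SAP narrows a promised analysis without declaring it. For time to onset, duration, action taken and outcome, and only for these four, the unblinded TI's attribution decides which events are summarised, and the control column in the CP should be empty. Incidence and maximum severity of all TEAEs by arm are not affected.

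The size cannot be put in participants. The documents give no AE rate and no share of events judged unrelated. A share of events would not convert to participants in any case, because someone with one related and one unrelated event stays in the related table. For controls the gap is structural: it covers every CP event in a planned arm of 40.

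The conclusion rests on three assumptions: that Table 5-7 is complete as the SAP's specification, that the unseen shells do not add these summaries, and that no control event is coded as related during the CP.

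**What to change.** In SAP Table 5-7, add the line "Overall summary by maximum severity, time to onset, duration, action taken and outcome" to the all-TEAE row. Present it by arm for the CP on the Safety Population, and for the initially treated (VITP) and optionally treated (VOTP) populations in the TP, with the treatment-related subset beneath it.

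State the time origin: initial treatment for the treatment group, randomization for untreated controls, and the optional initial treatment for VOTP. Add a footnote that the treatment arm's CP can run about 8 weeks longer than the control arm's when a touch-up is given. Check the table shells against the revised row.

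The cost is one line in the SAP and one longer descriptive table per period that includes unrelated background events. No new data are needed. If the sponsor prefers to keep the restriction, the minimum is to record it in Appendix 2 with a reason. That would declare the departure but would leave both the filter and the empty control column in place.
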